Skeletal tissue is highly responsive to mechanical stress;³⁷ thus, WL-associated declines in mechanical loading likely contribute to BMD loss.^{16,19} Clinical trial data consistently demonstrate that the addition of exercise training (designed to enhance gravitational or muscle loading³⁸⁻⁴¹) to intentional WL attenuates the amount of bone lost compared to WL alone.⁴²⁻⁴⁶ We recently reported resistance exercise training (RT) is superior to aerobic exercise training in attenuating WL-associated bone *and* muscle losses, while augmenting loss in total body fat mass.⁴⁷ However, RT was unable to *fully* prevent bone and muscle loss and, in agreement with prior findings,⁴⁸ intervention effectiveness hinged significantly on exercise compliance. Although intuitive, this observation may be especially important for older adults who are less likely⁴⁹ (i.e., unwilling or unable) to perform the volume and intensity of exercise necessary to preserve bone during WL. In addition, conventional RT often requires expensive equipment, on-site participation, and (ideally for older adults) safety supervision by trained staff, limiting its scalability as an intervention strategy.

Alternately, treating WL-associated decrease in mechanical load by replacing lost weight externally may also preserve bone mass. In animal models, skeletal metabolism responds in a similar fashion to increases in actual body, or externally added, mass.⁵⁰⁻⁵² In human studies, wearing weighted vests during exercise improves areal BMD (aBMD) and bone turnover, as well as muscle mass and lower extremity strength.⁵³⁻⁶¹ Our pilot data suggest this approach is both feasible and likely effective in reducing WL-associated hip aBMD loss by increasing bone formation.⁶² If confirmed, the greater availability, ease of administration, and reduced cost associated with weighted vest use to offset WL-associated bone loss, as compared to RT, holds significant public health potential as a translatable strategy to maximize the cardiometabolic benefits of WL, while minimizing potential harm to the musculoskeletal system.

Objectives

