The **main goal** of this study is to compare the effects of WL alone with WL plus weighted vest use or WL plus RT on indicators of bone health and subsequent fracture risk. This is a 12 month trial in 150 older (60-85 years) adults with obesity (BMI=30-40 kg/m² or BMI= 27.0-<30 kg/m² plus one risk factor) randomized to one of three interventions (n= 50/group): WL alone (**WL**; caloric restriction targeting 10% WL with adequate calcium, vitamin D, and protein); WL plus weighted vest use (**WL+VEST**; targeting 8 hours/day, weight replacement titrated up to 10% WL); or, WL plus structured RT (**WL+RT**; targeting 3 sessions/week). In Version 11.4.2022

accordance with recent international position statements on the clinical use of computed tomography (CT) of the hip in the management of osteoporosis,^{63,64} total hip trabecular volumetric BMD (vBMD) is the primary outcome. This outcome will be complemented by exploratory assessment of several fracture-related risk factors, including: (1) femoral neck and lumbar spine vBMD, cortical thickness, finite element modeling of bone strength, and regional fat and muscle volumes, measured by CT; (2) aBMD at the total hip, femoral neck, lumbar spine, and distal radius; trabecular bone score; and total body fat/lean masses, measured by dual energy x-ray absorptiometry (DXA); (3) muscle function and strength; (4) biomarkers of bone turnover; and (5) bone-regulating hormones/cytokines known to influence bone metabolism during WL. Therefore, our Specific Aims are to:

Aim 1: Determine the effects of WL+VEST compared to WL and WL+RT on 12 month change in total hip trabecular vBMD. Despite similar reductions in total body weight, **Hypothesis 1:** Participants in the WL+VEST group will show attenuated losses of total hip trabecular vBMD versus WL; and **Hypothesis 2:** Loss in total hip trabecular vBMD will be no greater in WL+VEST compared to WL+RT.

Aim 2: Explore the effects of WL+VEST compared to WL and WL+RT on the 12 month change in fracture-related risk factors. Despite similar reductions in total body weight, we **hypothesize** that WL+VEST and WL+RT will demonstrate improvements in fracture-related risk factors compared to WL.

Methods and Measures

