In addition to receiving dietary counseling, all participants will be asked to attend virtual or in-person behavioral counseling group sessions led by the RD. These sessions will be held weekly for the first 6 months and bi-weekly for the remainder of the study to provide participants an opportunity to review specific questions and problems. The education and counseling component of the intervention will emphasize instruction in making healthy, lower-calorie food choices while teaching changes in behavioral habits to promote WL and prevent weight regain.⁷³ Specific emphasis will be placed on the acquisition and use of self-management skills, particularly self-monitoring of diet and weight, and achieving 150 minutes of aerobic activity/week, in accordance with national guidelines.^{65,74} Throughout the 12 month WL phase, participants will be asked to track their food/beverage intake (including the number of meal replacements consumed each day) daily for the first three months and then on a reduced schedule as warranted. These will be reviewed routinely by the study registered dietitian. Body weight will be measured and recorded at all group sessions to provide additional feedback and to increase motivation. Official study weights will occur at SV3, FV2, and FV4. If it is evident (either through review of diet records or inadequate WL) that participants are struggling to meet their WL goals additional individual counseling sessions with the RD will be held to improve compliance. At FV1 and FV3, participants in this group will be asked to complete a program evaluation form to solicit feedback on overall WL program satisfaction, desired future usage, and product preferences. Periodically throughout intervention, participants will be asked to rate their confidence (i.e., self-efficacy) in meeting the demands of the intervention they are receiving. They will also be asked to report changes in their health and medication.

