calculated using the Weir equation. Accelerometry will be used to objectively assess physical activity over a seven day period at baseline, 6 and 12 months using a triaxial accelerometer and inclinometer.¹⁰⁵ Finally, questionnaires assessing fatigue/fatigability¹⁰⁶, pain¹⁰⁷, physical activity¹⁰⁸, and intervention adherence self-efficacy (with questionnaire specific to INVEST modeled on prior work¹⁰⁹) will be assessed. If covariates are found to be unbalanced between groups, and related to study outcomes, these variables will be included as covariates in exploratory, secondary statistical analyses. Lastly, adverse events will be assessed and recorded by asking participants to complete a bi-monthly health status questionnaire. Spontaneously reported adverse events will also be collected and reported by study staff.

Data and Statistical Analyses

Data Management. Data will be collected on forms at the clinic site and transferred to a secure electronic database. Our web-based management system will assure integrity and validity. Dynamic reports and statistical analyses will monitor quality. A participant-based inventory system will track recruitment, retention, adherence, and missing data from entry through exit, close-out, and lock-down of final datasets.

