Statistical Analyses. We will use intention-to-treat principles in full accordance with CONSORT guidelines. We will monitor serious adverse events regularly to maintain up-to-date safety information for reporting to the DSMB. All data will undergo range checks at the time of data entry and will be examined monthly by histograms and bivariate scatterplots to check for inconsistencies, unusual data needing further verification, and outliers. Plots of longitudinal observations will be used to inspect for unusual changes requiring verification against source documentation. Regression diagnostics and exploratory analyses will be performed to find appropriate transformations of variables if needed. Order of priority in choosing a transformation will be to satisfy: 1) linearity, 2) homogeneity, and 3) normality assumptions. We will attempt to identify baseline covariates that predict attrition and compliance; and if such covariates can be identified, the analyses may need to incorporate stratification by these factors to decrease bias. In addition, following the recommendations of the 2010 National Academy of Sciences report,¹¹⁰ if the outcome is found to be missing at random, we will attempt to identify baseline covariates that predict attrition and use these covariates to impute missing data based on multiple imputation. Sensitivity analyses, using methods like pattern mixture models, will be carried out to explore the effect of missing outcomes on inference (if found to be not at random). Additionally, we will conduct sensitivity analyses of efficacy taking into account treatment compliance as a binary (compliers defined as >80% of prescribed vest wear time, >80% resistance training attendance, >80% of weight loss target) or continuous variable (proportion of treatment received).

Sample Size and Power. A total sample size of 150 (n=50 per group) is optimal to test hypotheses for the primary study aims. Using co-primary hypotheses demands use of a conservative Bonferroni correction of dividing the Type I error rate (α) in half for each aim to determine statistical significance.

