established at $p<0.025$. Next, the noninferiority of WL+VEST compared to WL+RT will be determined based on whether the lower bound of the one-sided confidence interval for the estimated 12 month treatment effect of WL+VEST versus WL+RT overlaps the -4.0% non-inferiority boundary for total hip trabecular vBMD. This will be performed using $\alpha=0.0125$ to account for co-primary hypotheses as well as for using a 1-sided alternative hypothesis. Tests for both co-primary hypotheses will be based on different contrast statements from the same statistical model. Secondarily, we will repeat these analyses with the short-term effect at 6 months of both interventions as an exploratory analysis. For Aim 2, we will repeat these analyses for the 12 month effect (and secondarily 6 month effect) using total hip aBMD assessed by DXA as the outcome. Comparisons will be performed for both superiority of WL+VEST vs. WL as well as noninferiority of WL+VEST vs WL+RT based on a 2.13% noninferiority margin using the methods described above. Analytic models for all other Aim 2 outcomes will mirror the model used in the primary aim, with the important exception that comparisons will focus on statistical comparisons of group mean differences. All outcomes are assessed at 6 and 12 months, and while both visit time points will be estimated, the 12 month treatment effect will be considered of primary interest. Treatment effects for changes in outcome variables are compared using a mixed model fit with treatment group, visit, and treatment by visit interaction, adjusted for sex and baseline values of the outcome. Tests will be performed using contrast statements at 12 months (primarily) and 6 months (secondarily), and we will use the partial F-test $p<0.05$ for significance. Significant comparisons for secondary outcomes will further use comparisons of all three groups at each visit using $p<0.0167$ for pairwise significance. Lastly, we intend to explore the associations between 6 and 12 month change in vBMD or aBMD with change in secondary outcome measures (i.e., DXA and CT-acquired body composition, D3Cr muscle mass, biomarkers of bone turnover, bone regulating hormones/cytokines) using linear regression methods and adjusted for sex and treatment group, to explore potential mechanisms underlying the treatment effect. Secondary comparisons will not be adjusted for multiplicity other than for pairwise group comparisons. Statistical analyses will be conducted using SAS v9.4 (SAS Institute, Cary, NC) and R software.

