Safety measures during the interventions: For the dietary intervention, all study participants are monitored for compliance to a safe level of caloric deficit. Since the degree of bone and muscle loss is accelerated by the rate of weight loss, all participants will be weighed weekly and if weight is being lost at a rate greater than 0.9 kg/wk (~2 lb/wk), adjustments may be made to the meal plan to increase the level of calories recommended to slow down this excess rate of weight loss. As stated previously, at the outset of all group sessions, participants will be queried regarding problems or health symptoms they may be experiencing with the vest. The interventionist will record the presence or absence of such symptoms and determine whether or not the problem requires medical attention and, if so, to determine whether or not the contact should be handled emergently or, in consultation with the study physician, by a scheduled appointment with the primary care provider. Supervised RT sessions are conducted at a central location and are supervised by trained interventionists who monitor potential adverse experiences and symptoms. On-site staff trained in advanced cardiac life support are available to deal with medical emergencies. Also, institutional and community EMS services will be activated if needed. Procedures to minimize musculoskeletal discomfort to the exercise include teaching proper warm-up and cool down activities and providing instruction on correct exercise techniques and fall safety. If for any reason the participant reports a fall or other injury, or chest pain, shortness of breath, or dizziness, during a supervised RT session, they will be referred to their doctor, or study staff will notify the participant's doctor or other health care provider with their permission. If at any point during a RT session, participants develop chest pain, shortness of breath, or dizziness, they will be instructed to stop exercise, and to contact the study staff if these symptoms persist or recur. We monitor blood pressure and heart rate before and after all supervised RT sessions. If an intervention-related injury or illness does occur, the study medical staff will be consulted according to the type of symptom reported. In some instances, it may be appropriate to reduce or to temporarily suspend the participant's weight loss, vest use, or RT goals. If the injury or symptoms do not resolve after an appropriate period of time, the participant will be referred to his/her primary care provider for further evaluation. The participant will be encouraged to follow the primary care provider's instructions regarding intervention compliance.

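### The exploratory mechanism regressions leave out weight change, so a circulating marker that only tracks weight lost can be taken for a mechanism

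*Combined protocol and SAP*

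**What the plan says.** The last part of the Statistical Analysis Plan states the intention to "explore the associations between 6 and 12 month change in vBMD or aBMD with change in secondary outcome measures". The measures named are body composition by DXA and CT, muscle mass by labelled creatine, bone turnover biomarkers, and bone-regulating hormones and cytokines. The models are fitted "using linear regression methods and adjusted for sex and treatment group, to explore potential mechanisms underlying the treatment effect". No other covariate is listed, no significance level is given for these models, and the plan does not say whether measures enter singly or together. Secondary comparisons carry no multiplicity adjustment beyond that for pairwise group contrasts.

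Elsewhere the document links weight loss to bone:

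- Safety measures during the interventions: "Since the degree of bone and muscle loss is accelerated by the rate of weight loss".
- Background: "WL-associated declines in mechanical loading likely contribute to BMD loss".
- Objectives: both aims are framed "Despite similar reductions in total body weight" across arms.
- Weight Loss Intervention: "Official study weights will occur at SV3, FV2, and FV4", which are the baseline, 6-month and 12-month visits.

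**The concern.** Once treatment group is in the model, the coefficient of a marker is estimated from differences among participants within an arm. Those participants will have lost different amounts of weight. If weight lost is related to bone change and also to the marker, the two changes will be correlated even when neither affects the other. The arm term does not prevent this: it removes only differences between arm means, and the protocol expects those to be small for weight.

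The stated purpose is to explore how the interventions act on bone. A marker that only records how much weight someone lost says nothing about why a vest or resistance training might protect bone. With no general multiplicity control, little else in the plan would filter out such a lead.

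**Working it through.** The plan gives no power, level or expected correlation for these regressions, so there is no stated figure to reproduce.

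**Inputs from the document.** Completers: 128 (Methods and Measures, recruitment paragraph; 150 × 0.85 = 127.5). Adjustment set: sex and arm.

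**Assumptions.** Two-sided 0.05, the level used for the other Aim 2 tests. Within-arm correlations of weight change with bone change, r(W,B), and with marker change, r(W,M). No direct link between marker and bone.

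**Step 1: induced correlation.** With weight change as the only connection, r = r(W,B) × r(W,M).

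**Step 2: chance of p < 0.05.** By Fisher's z, with 4 degrees of freedom allowed for covariates (one more than sex and arm use, which is immaterial), SE = 1/√(128 − 4 − 3) = 1/11 = 0.0909. The chance is about P(Z > 1.96 − atanh(r)/SE).

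| r(W,B) | r(W,M) | r | atanh(r)/SE | Chance flagged |
|---|---|---|---|---|
| 0.3 | 0.4 | 0.12 | 1.33 | 26% |
| 0.4 | 0.5 | 0.20 | 2.23 | 61% |
| 0.5 | 0.6 | 0.30 | 3.40 | 93% |

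**Step 3: simulation.** 10,000 trials per setting, n = 128, three arms and sex. Chance that the marker is flagged under the planned adjustment:

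| r(W,B) | r(W,M) = 0.3 | 0.5 | 0.7 | 0.9 |
|---|---|---|---|---|
| 0 | 5% | 5% | 5% | 5% |
| 0.2 | 11% | 20% | 35% | 51% |
| 0.3 | 17% | 39% | 66% | 87% |
| 0.4 | 27% | 61% | 89% | 99% |
| 0.5 | 39% | 81% | 98% | about 100% |

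With weight change added, the rate is 4.5% to 5.4% in every cell.

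**Step 4: do other rules in the plan cover this?** The covariate rule under Descriptive Data, Potential Covariates, and Adverse Events reads "If covariates are found to be unbalanced between groups, and related to study outcomes, these variables will be included as covariates". It is triggered by imbalance between groups, which the hypotheses do not expect for weight, and balance between arms does not deal with confounding within them. Under Statistical Analyses, "we will conduct sensitivity analyses of efficacy taking into account treatment compliance as a binary" or continuous variable includes the weight loss target, but it concerns efficacy. Neither reaches the mechanism models.

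**Step 5: does the same remedy suit fat and lean mass?** No. Weight change W is roughly fat change F plus lean change L. If bone change depends on lean alone, B = bL + e, then B ≈ b(W − F) + e, and a model with F and W gives fat a coefficient near −b although fat has no effect. Simulations with n = 128, using for example SDs of 4 (fat) and 1.5 (lean) and a lean–bone correlation of 0.3, all assumed, gave these false flags for fat:

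| Fat–lean correlation | Planned model | With weight change |
|---|---|---|
| 0.2 | 10% | 72% to 80% |
| 0.4 | 28% | 59% to 65% |
| 0.6 | 52% | 40% |

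The last column falls as weight change departs from an exact sum of fat and lean. In this scenario a model with fat and lean together is correctly specified, so the false-flag rate for fat is the nominal 5%.

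**The case against.** The strongest objection is that weight change is not a common cause of everything on the list. For fat, lean and muscle mass it is close to a sum of the candidate exposures, and step 5 shows that adjusting for it can create an association. This stands, and it limits the remedy to circulating markers.

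Second, the document says less than one might read into it. A reader might infer that weight loss is the main thing that differs within an arm, or that all the markers follow it. The safety section speaks only of bone and muscle, and of acceleration; the background says reduced loading likely contributes. The compliance analyses expect vest wear and training attendance to vary as well. That circulating markers track weight lost is therefore an assumption, although the Objectives choose the hormones and cytokines for their role in bone metabolism during weight loss.

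Third, the vest is meant to replace lost load, so the relation of weight loss to bone may be weaker in that arm. A single pooled correlation, and a single weight covariate, ignore this. It affects the size of the problem rather than its direction.

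Fourth, if fat and lean change entered jointly with a marker, most of weight change would already be absorbed. The plan does not specify such a model.

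Finally, the work is labelled exploratory, and no hypothesis or power claim rests on it. That stands and sets the weight of the point.

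**Conclusion.** The point holds for bone turnover biomarkers and bone-regulating hormones and cytokines. As specified, the model cannot separate a marker that acts on bone from one that only follows weight lost. Under the assumed correlations (0.3 to 0.5 for bone, 0.4 to 0.6 for the marker) and the assumed 0.05 level, a marker with no direct link is flagged in about 26% to 93% of trials with 128 completers, against about 5% with weight change in the model. If weight change were unrelated to bone change the excess would vanish, but the protocol's own rationale is that they are related.

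Three stronger readings are not supported. The weight-adjusted coefficient is not the right answer for every measure; for body composition it can mislead. The absence of baseline values is not a demonstrated fault: the treatment models include the baseline outcome in order to compare randomised groups, and that practice does not carry over automatically to regressing one change on another. Nor does anything here touch the primary superiority and noninferiority tests.

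**What to change.** Add to the Statistical Analysis Plan, before results are seen:

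- For bone turnover biomarkers and bone-regulating hormones and cytokines, report each coefficient without and with percent weight change over the same interval (0 to 6 or 0 to 12 months), from the official weights at SV3, FV2 and FV4. Interpret the two together, and do not describe an association that disappears after adjustment as a mechanism separate from weight loss.
- For fat, lean and muscle mass measures, do not make the weight-adjusted model the preferred one. Enter fat and lean change jointly.

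The cost is one covariate already collected, a second column in the tables and some loss of precision. If weight loss acts on bone through the marker, the adjusted coefficient answers a narrower question, namely the association at a given weight loss, which is why both should be shown. Even then, a within-arm association is not a mediation analysis of the difference between arms, and the report should say so.

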Weight Loss + Structured Resistance Exercise Training Intervention (WL+RT). The WL component of the intervention is described above. Participants assigned to the WL+RT group will undergo a progressive RT intervention designed to elicit adaptations in the musculoskeletal system. Exercise sessions will take place on three non-consecutive days/week, and will be supervised by staff exercise trainer also trained in basic life support and emergency management procedures. The RT program is based on recent guidelines with respect to intensity, number of repetitions, exercises, sets, and days per week.⁷⁸ The maximal weight that can be lifted with correct form in a single repetition (1RM) will be used to prescribe intensity. Progression of intensity, repetitions and sets will be individualized and gradual to allow participants to familiarize themselves with the equipment, minimize muscle soreness and reduce potential for injury. The training goal is for participants to complete three sets of 10-12 repetitions for 8 different exercises at 70-75% 1RM for that given exercise. Participants will be instructed to rest for approximately one minute between each set. The resistance will be incremented when a participant can complete 12 repetitions for two of three sets on two consecutive sessions. Heart rate and blood pressure will be measured before and after each session. Participants will be instructed to warm-up at the start of each session by walking or cycling for 5-10 minutes at a slow pace, and will end each session with a cool-down of light stretching. The interventionists will ensure that participants adjust the equipment appropriate to their body size and complete the exercises with correct form.

Methods for Study Assessments

Table 3 provides a detailed study assessment timeline. The nature, purpose, and risks of all procedures and protocols will be explained to each participant prior to obtaining written consent. All examiners are trained in the standardized conduct of all assessments before data collection. Participants will be instructed to wear appropriate and comfortable clothing, and standardized written instructions will be provided prior to each study visit.

INVEST Measurements	PS	SV1	SV1-A	SV2	SV3	INT	FV1	FV2	INT	FV3	FV4	SV3, INT, FV2, FV4
Participant Status		fasting			fasting			fasting			fasting	
Weeks			-8 to 0			1-24	22-26		25-52	50-54		
Location		WFSM or WFU	Phone	WFU	WFSM	WFSM or WFU	WFU	WFSM	WFSM or WFU	WFU	WFSM	Phone
Questionnaires												

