
Statistical Analysis and Power Considerations for Limb Loading Sub-Study:

Limb Loading Analysis: Data from the insoles will be downloaded from the smartphone and imported into MATLAB (Mathworks Inc, Natick, MA, USA). Limb loading outcomes will include peak impact force, loading rate, impulse, and cumulative loading. Peak impact force will be calculated as the largest peak in the first 25% of all foot contacts. Loading rate will be calculated as the peak impact force divided by the time to reach the peak impact force from initial foot contact ($>10N$). Impulse for each foot contact (e.g. step, exercise repetition) is the area under the force curve. Cumulative loading will be defined as the total impulse from all recorded foot contacts. These outcomes will be determined for the right limb and will be averaged for each day of use with the daily average for each metric used for data analysis.

Femoral Stress and Strain Analysis: The baseline subject-specific proximal femur models developed in the parent study will be utilized for the proposed pilot to conduct additional FE simulations that prescribe the insole daily limb loads to estimate *in vivo* femoral stress and strain. The “peak impact force daily average” and “loading rate daily average” measured by the insoles will be applied to the femoral head of the FE model by prescribing a “force vs. time” curve that ramps up to the peak impact force in the time from initial foot contact (time=peak impact force divided by loading rate). The maximum femoral stress and femoral strain attained during the simulation will be output from the proximal femur, along with the location of those elements (e.g. femoral neck, trochanter, shaft). A strain of approximately 0.04 – 0.10% is estimated to be the minimum effective strain required to prevent bone loss. Strain values derived from our simulation will be compared to these values to determine if daily limb loading imposes adequate strain for maintenance of BMD.

Feasibility Analysis: Feasibility of wearing force-sensing insoles will be assessed by recruitment, adherence, and satisfaction. Recruitment rates and adherence to wearing the insoles over 4 days will be recorded, and overall satisfaction will be measured with an overall satisfaction questionnaire.

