To evaluate limb loading, an analysis of covariance (ANCOVA) to test for mean differences between groups in daily loading metrics (cumulative loading, peak force, loading rate, impulse). To evaluate femoral stress and strain, an ANCOVA will also be used with femoral mechanical stress and strain as the dependent variable. In the event of significant differences, post-hoc independent two-sample t-tests using a Bonferroni adjusted alpha = 0.025 will further be tested. Fifteen participants per group provides 80% power to detect a moderate effect size (Variance between/Variance within) of 0.40 using a 0.05 Type I error rate and 87% retention at 6 months. Cohen's *d* effect sizes will be calculated to further contextualize group differences and inform future sample size calculations. Pearson product moment will also explore associations between daily limb loading metrics, change in areal and volumetric BMD, and changes in physical function separately by group and across all groups combined.

Human Subjects Protection

Subject Recruitment Methods: We will recruit individuals using community-based recruitment strategies including newspaper ads and mass mailings. We will also advertise in the Sticht Center recruitment newsletter (Volunteers in Touch with an Active Lifestyle: VITAL), utilize WakeOne recruitment letters, and participate in community outreach events.

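### Limb-loading sub-study: daily averages of peak force and loading rate give resistance-training repetitions little weight, and no covariate is named to remove body-mass variation from the arm comparisons

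*Combined protocol and SAP*

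**What the plan says.** All references are to the combined protocol and SAP, mainly the section on statistical analysis and power for the limb-loading sub-study.

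- **Peak force** (Limb Loading Analysis): "Peak impact force will be calculated as the largest peak in the first 25% of all foot contacts".
- **Loading rate:** "Loading rate will be calculated as the peak impact force divided by the time to reach the peak impact force from initial foot contact". Neither metric is scaled to body weight.
- **What counts as a contact:** "Impulse for each foot contact (e.g. step, exercise repetition) is the area under the force curve".
- **Cumulative loading:** "Cumulative loading will be defined as the total impulse from all recorded foot contacts".
- **Reduction to analysis values:** right-limb metrics "will be averaged for each day of use with the daily average for each metric used for data analysis".
- **Use in the strain model** (Femoral Stress and Strain Analysis): the daily averages of peak force and loading rate "measured by the insoles will be applied to the femoral head of the FE model". The resulting strain is compared with a minimum effective strain of roughly 0.04-0.10%.
- **Test** (paragraph after Feasibility Analysis): "an analysis of covariance (ANCOVA) to test for mean differences between groups in daily loading metrics", and an ANCOVA for stress and strain. No covariate is named. Significant results are followed by independent two-sample t-tests at alpha 0.025.
- **Size:** 15 per group, 80% power for a variance ratio of 0.40, alpha 0.05, 87% retention at 6 months.
- **RT volume** (WL+RT intervention): "three sets of 10-12 repetitions for 8 different exercises", three days a week.

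**The concern.** There are two separate issues.

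First, a mean over a day's contacts is governed by the commonest contact, which is an ordinary step. An RT session adds a limited number of loaded contacts on three days a week. The vest, worn up to 8 hours a day, acts on every step taken while it is on. A mean of peak force or loading rate therefore registers the vest far more readily than RT. Because the same daily means drive the strain simulation, the highest RT loads are averaged away before strain is judged against the threshold.

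Second, absolute force depends on body mass. The trial enrols men and women with BMI 27-40. If mass is not in the model, that spread sits in the error term at about 13 per arm. The parent-trial models name sex and the baseline value; the sub-study names nothing, and its post-hoc t-tests would discard any covariate the ANCOVA did contain. The plan intends Cohen's d from this pilot to inform future sample sizes, so a diluted and unadjusted d would carry forward.

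**Working it through.** **1. The plan's own power figure.** n = 15 x 0.87 = 13.05, taken as 13 per group; three groups; df 2 and 36. With the variance of means using divisor G-1, lambda = n(G-1) x 0.40 = 13 x 2 x 0.40 = 10.4. The noncentral F gives 79.7%, so the stated 80% reproduces. A ratio of 0.40 corresponds to a pairwise difference of 1.10 SD (one arm differs) to 1.26 SD (evenly spaced means).

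**2. Weight of RT repetitions in a daily mean.**

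From the plan: 3 x 10 x 8 = 240 to 3 x 12 x 8 = 288 repetitions per session over all exercises. This is an upper bound, since not every exercise loads the foot.

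Assumed: half of them, 120-144, load the foot; 2,000-3,000 right-foot contacts a day; repetition peak force k = 1.5-2 times a step.

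Relative rise on a session day = reps x (k - 1) / (steps + reps).

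- Lowest: 120 x 0.5 / 3,120 = 1.9%
- Highest: 144 x 1.0 / 2,144 = 6.7%

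Over four wear days with one or two sessions:

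- Lowest: 1.9% x 1/4 = 0.5%
- Highest: 6.7% x 2/4 = 3.4%

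Wider inputs (72-288 repetitions, 1,500-4,000 contacts, k = 1.5) give 0.9-8% on a session day and 0.4-3.5% averaged over a week with three sessions.

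For comparison, if force follows carried mass, full replacement of a 10% loss gives vest minus WL alone = 0.10/0.90 = 11.1%. If only 50-75% of contacts occur with the vest on (assumed), this becomes 5.6-8.3%.

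**3. Body mass in the error term.**

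The documents give no SD for any loading metric. A uniform BMI from 27 to 40 has CV = (13/sqrt(12))/33.5 = 11.2%. With mass = BMI x height squared and an assumed height CV of 4-6%, mass CV = sqrt(0.112^2 + (2 x 0.04)^2) = 13.8% to sqrt(0.112^2 + (2 x 0.06)^2) = 16.4%. I use 12-18% to bracket this.

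Further assumptions: force proportional to mass; residual CV 10, 15 or 20%; a 10% arm difference; 13 per arm; two-sided alpha 0.025. Unadjusted d = 0.10/sqrt(massCV^2 + residCV^2). Adjusted d = 0.10/residCV, which supposes the covariate removes all the mass variance and is therefore a best case. Power is from the noncentral t on 24 df.

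| Residual CV | Unadjusted d (mass CV 18% to 12%) | Unadjusted power | Adjusted d | Adjusted power |
|---|---|---|---|---|
| 10% | 0.49 to 0.64 | 14-24% | 1.00 | 57% |
| 15% | 0.43 to 0.52 | 11-16% | 0.67 | 26% |
| 20% | 0.37 to 0.43 | 9-12% | 0.50 | 15% |

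Every d in the table is below the 1.10-1.26 SD for which the sub-study is powered.

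**The case against.** Several points on the other side stand and limit the claim.

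- **Not every metric is diluted.** A reader might infer that the sub-study can barely detect RT loading. It does not follow: cumulative loading is a total over contacts, so repetitions add to it in full. Nor does the argument reach impulse. Impulse includes contact duration, and a slow loaded repetition may last much longer than a step. If its impulse were 3-5 times a step (assumed), mean impulse on a session day would rise by 120 x 2 / 3,120 = 8% to 144 x 4 / 2,144 = 27%.
- **The wording is not fully explicit.** The peak-force sentence could mean the first quarter of each contact or the first quarter of the contacts. Averaging over contacts is the natural reading, supported by the daily-average terms used for the strain model, but it is a reading.
- **A daily mean answers a fair question.** The sub-study asks whether daily loading produces adequate strain, and the vest is meant to sustain loading through the day. The mean is a legitimate summary of that; it is incomplete for RT rather than biased.
- **Adjustment is not ruled out.** ANCOVA implies some covariate, and the section on potential covariates allows unbalanced, outcome-related variables into exploratory analyses. What the text shows is that no covariate is named and that the post-hoc tests are unadjusted.
- **Body mass does not hide the vest effect.** That reading is too strong. At residual CV 10% the 10% difference is about 1.2-1.6 standard errors (d x sqrt(13/2)): underpowered, not invisible. The gain from adjustment also shrinks quickly as residual variation grows.

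**Conclusion.** The point holds for peak impact force, loading rate and the strain derived from them. Under the stated assumptions RT moves the daily mean of the first two by about 2-7% on a session day and 0.5-3.4% over four wear days. Separately, leaving baseline mass and sex unnamed, and testing pairs with plain t-tests, gives up precision that is available from data already collected: at alpha 0.025, 57% rather than 14-24% power at residual CV 10%, narrowing to 15% rather than 9-12% at 20%.

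Step counts, foot-loading repetitions, force multiples and CVs are all assumptions; the documents supply none of them. They also do not say whether the four wear days include an RT session. No claim is made about cumulative loading or impulse. The matter is confined to a pilot sub-study, so it is a worthwhile refinement rather than a defect in the main trial.

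**What to change.** 1. Name baseline body mass and sex as covariates in every loading, stress and strain ANCOVA. Sex is already a randomisation stratum and mass is already measured. Use baseline rather than current mass, so that lost or replaced weight stays in the arm contrast.
2. Replace the post-hoc two-sample t-tests with pairwise contrasts from the same adjusted model at alpha 0.025.
3. Keep raw force as the input to the finite element model.
4. State that peak force and loading rate are computed per contact and then averaged over the day, if that is the intention.
5. As exploratory additions, report the daily 95th percentile of per-contact peak force and loading rate. Where recordings can be matched to session times, also summarise RT-session contacts separately.

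Cost: SAP wording and analysis code, two degrees of freedom out of about 36, and a few more exploratory metrics. The 95th percentile is only a partial remedy. It moves little when repetitions are under 5% of the day's contacts (120/3,120 = 3.8% at the low end above) and does not register RT on days without a session. The session split depends on contacts being identifiable by session, which the documents do not state.
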